8.2 DATA QUALITY ASSURANCE

A risk-based approach is used for trial quality management. It is initiated by the assessment of critical data and processes for trial subject protection and reliability of the results as well as identification and assessment of associated risks. An Integrated Quality and Risk Management Plan documents the rationale and strategies for risk management during trial conduct including monitoring approaches, vendor management and other processes focusing on areas of greatest risk.

Continuous risk review and assessment may lead to adjustments in trial conduct, trial design or monitoring approaches.

A quality assurance audit/inspection of this trial may be conducted by the sponsor, sponsor's designees, or by IRB / IEC or by regulatory authorities. The quality assurance auditor will have access to all medical records, the investigator's trial-related files and correspondence, and the informed consent documentation of this clinical trial.

8.3 RECORDS

CRFs for individual subjects will be provided by the sponsor. See section [4.1.6.2](#) for rules about emergency code breaks. For drug accountability, refer to section [4.1.9](#).

8.3.1 Source documents

In accordance with regulatory requirements, the investigator should prepare and maintain adequate and accurate source documents and trial records that include all observations and other data pertinent to the investigation on each trial subject. Source data as well as reported data should follow the "ALCOA principles" and be **attributable, legible, contemporaneous, original and accurate**. Changes to the data should be traceable (audit trail).

Data reported on the CRF must be consistent with the source data or the discrepancies must be explained.

The current medical history of the subject may not be sufficient to confirm eligibility for the trial and the investigator may need to request previous medical histories and evidence of any diagnostic tests. In this case, the investigator must make at least one documented attempt to retrieve previous medical records. If this fails, a verbal history from the subject, documented in their medical records, would be acceptable.

Before sending or uploading those copies, the investigator must ensure that all subject identifiers (e.g. subject's name, initials, address, phone number, social security number) have properly been removed or redacted from any copy of the subjects' source documents.

If the subject is not compliant with the protocol, any corrective action e.g. re-training must be documented in the subject file.

For the CRF, data must be derived from source documents, for example:

- Subject identification: gender, year of birth (in accordance with local laws and regulations)
- Subject participation in the trial (substance, trial number, subject number, date subject was informed)
- Dates of subject's visits, including dispensing of trial medication
- Medical history (including trial indication and concomitant diseases, if applicable)
- Medication history
- Adverse events and outcome events (onset date (mandatory), and end date (if available))
- Serious adverse events (onset date (mandatory), and end date (if available))
- Concomitant therapy (start date, changes)
- Originals or copies of laboratory results and other imaging or testing results, with proper documented medical evaluation (in validated electronic format, if available)
- Completion of subject's participation in the trial" (end date; in case of premature discontinuation document the reason for it).
- Prior to allocation of a subject to a treatment into a clinical trial, there must be documented evidence in the source data (e.g. medical records) that the trial subject meets all inclusion criteria and does not meet any exclusion criteria. The absence of records (either medical records, verbal documented feedback of the subject or testing conducted specific for a protocol) to support inclusion/exclusion criteria does not make the subject eligible for the clinical trial.

Originals or copies of laboratory results and other imaging or testing results (with proper documented medical evaluation (in validated electronic format, if available) will be electronically transferred and uploaded into the trial database.

8.3.2 Direct access to source data and documents

The investigator /institution will allow site trial-related monitoring, audits, IRB / IEC review and regulatory inspections. Direct access must be provided to the CRF and all source documents/data, including progress notes, copies of laboratory and medical test results, which must be available at all times for review by the CRA, auditor and regulatory inspector (e.g. FDA). They may review all CRFs and informed consents. The accuracy of the data will be verified by direct comparison with the source documents described in section [8.3.1](#). The sponsor will also monitor compliance with the protocol and GCP.

8.3.3 Storage period of records

Trial site(s):

The trial site(s) must retain the source and essential documents (including ISF) according to contract or the local requirements valid at the time of the end of the trial (whatever is longer).

Sponsor:

The sponsor must retain the essential documents according to the sponsor's SOPs.

8.4 EXPEDITED REPORTING OF ADVERSE EVENTS

BI is responsible to fulfil their legal and regulatory reporting obligation in accordance with regulatory requirements.

8.5 STATEMENT OF CONFIDENTIALITY AND PATIENT PRIVACY

Data protection and data security measures are implemented for the collection, storage and processing of subject data in accordance with the principles 7 and 12 of the WHO GCP handbook.

Individual subject data obtained as a result of this trial is considered confidential and disclosure to third parties is prohibited with the following exceptions:

Personalised treatment data may be given to the subject's personal physician or to other appropriate medical personnel responsible for the subject's welfare. Data generated at the site as a result of the trial need to be available for inspection on request by the participating physicians, the sponsor's representatives, by the IRB / IEC and the regulatory authorities.

8.5.1 Collection, storage and future use of biological samples and corresponding data

Not applicable.

8.6 TRIAL MILESTONES

The **start of the trial** is defined as the date when the first subject in the whole trial signs informed consent.

The **end of the trial** is defined as the date of the last visit of the last subject in the whole trial ("Last Patient Completed").

The "**Last Patient Last Treatment**" (LPLT) date is defined as the date on which the last subject in the whole trial is administered the last dose of trial treatment (as scheduled per

protocol or prematurely). Individual investigators will be notified of SUSARs occurring with the trial medication until 30 days after LPLT at their site.

Early termination of the trial is defined as the premature termination of the trial due to any reason before the end of the trial as specified in this protocol.

Temporary halt of the trial is defined as any unplanned interruption of the trial by the sponsor with the intention to resume it.

Suspension of the trial is defined as an interruption of the trial based on a Health Authority request.

The IEC / CA in each participating EU member state will be notified about the trial milestones according to the respective laws.

A final report of the clinical trial data will be written only after all subjects have completed the trial in all countries (EU or non-EU) to incorporate and consider all data in the report.

The sponsor will submit to the EU database a summary of the final trial results within one year from the end of a clinical trial as a whole, regardless of the country of the last subject (EU or non-EU).

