- Next recommended dose by the BLRM = current dose
- At least 12 subjects have been treated in the trial
- At least 6 subjects have been treated at the MFD

Part B of the study will only start if the highest dose is tolerated. Once the last subject in the highest dose cohort of Part A has attended visit 5 (day15) the SMC will meet and evaluate all

DLE data as well as available systemic and ophthalmological safety data. The decision on whether to proceed to Part B will be taken based on the occurrence of DLEs.

Part B:

In Part B, the highest dose will be used (██████). Thirty subjects will be recruited, 2:1 ratio of active treatment versus sham. Subjects dosed in Part A of the trial will not be included.

Subjects will be randomized to receive either active treatment or sham injection.

In Part B, subjects will receive three consecutive doses/sham injections over a 3-month period (██████████). All subjects included in the part B of the trial, will be observed for safety and efficacy for 12 weeks after the last injection.

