3.3 SELECTION OF TRIAL POPULATION

This trial will recruit up to 48 subjects in total; up to 18 subjects in Part A (depending on the dose escalation) and 30 subjects in Part B. In Part B subjects will be randomized to receive either active IVT injection or sham injection.

Screening of subjects for this trial is competitive, i.e. screening for the trial will stop at all sites at the same time once a sufficient number of subjects have been screened. Investigators will be notified about screening completion and will then not be allowed to screen additional subjects for this trial.

A log of all subjects enrolled into the trial (i.e. who have signed informed consent) will be maintained in the Investigator Site File (ISF) at the investigational site irrespective of whether they have been treated with the investigational drug or not.

Subjects who do not fulfil all eligibility criteria for a reason that later resolves allowing eligibility criteria to be met after the initial screening visit, can be re-screened up to one time.

If a subject is entered in error (does not meet all inclusion criteria or meets one or more exclusion criteria on the day of enrolment), the sponsor has to be contacted immediately. It is planned to conduct the trial in up to 3-6 countries and at approximately 50 sites.

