4.1.2 Selection of doses in the trial and dose modifications

Three doses [REDACTED] are planned in Part A. Part B will use the highest dose [REDACTED].

BI 765128 was injected intravitreally in New-Zealand White rabbits. Ocular tissues as well as plasma were sampled over a 14-day period and half-lives in the different tissues were

calculated. [REDACTED] and is, thus, also expected to be similar to [REDACTED] in humans. An IVT half-life in humans of 9.7 days has been described for [REDACTED] (R18-2968) and was assumed for BI 765128. The parameters to calculate the minimum effective vitreal concentration were based on the following assumptions: [REDACTED]

Using these values, the proposed therapeutic dose of [REDACTED] mg/eye is predicted to maintain the minimal efficacious vitreal concentration of 1000 pM (1 nM) for three months. Doses lower than [REDACTED] mg are also expected to induce PD effects in the eye. However, the duration of the effect would be shorter and might not provide sufficiently long potential benefit to the subjects.

The proposed escalation of the doses [REDACTED] is predicted to prolong the time for IVT antibody concentrations above the estimated minimally efficacious concentration, potentially allowing for longer dosing intervals. The starting dose and dose escalation were chosen based on the safety margin to the highest tested dose level [REDACTED] mg/eye) that did not result in adverse effects directly attributed to BI 765128, in the 13-week IVT toxicology study in cynomolgous monkeys.

Table 4.1.2: 1 Provisional dose levels for escalation

Dose level	[REDACTED]	[REDACTED]
[REDACTED]	[REDACTED]	[REDACTED]
[REDACTED]	[REDACTED]	[REDACTED]
[REDACTED]	[REDACTED]	[REDACTED]

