6.2.2 Treatment period(s)

For Part A, masking is not required for the IVT injection preparation or administration. For Part B, IVT injection will be prepared by the unmasked pharmacist/qualified person (Section 4.1.6). In addition, an unmasked injector (Section 4.1.6) with no other involvement in the trial will administer either active or sham injection according to the treatment assigned by IRT. IVT injections must be carried out according to medical standards and applicable guidelines by a qualified physician experienced in administering IVT injections and will be done as part of drug administration visit procedures (Visit 2 for Part A and Visits 2, 3 and 4 for Part B) after the other ophthalmologic assessments in the [Flow Chart I](#) and [Flow Chart II](#) have been performed (please see Section 4.1 for details).

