7.3.5 Safety analyses

Adverse events will be coded using the Medical Dictionary for Drug Regulatory Activities (MedDRA). Standard BI summary tables and listings will be produced. For BI 765128, the residual effect period (REP) after IVT administration is not known. Therefore, all AEs with an onset between start of treatment and the respective EOS visit will be assigned to the ontreatment period for evaluation. The safety analysis will be performed by planned dose group.

All treated subjects will be included in the safety analysis. In general, safety analyses will be descriptive in nature and will be based on BI standards. No hypothesis testing is planned.

Statistical analysis and reporting of adverse events will concentrate on treatment-emergent adverse events, i.e. all adverse events occurring between start of treatment and end of the EOS. Adverse events that start before first drug intake and deteriorate under treatment will also be considered as 'treatment-emergent'.

For all analyses the treatment actually administered (= treatment at onset) to the subject will be used (any deviations from the randomized treatment will be discussed in the minutes of the Report Planning Meeting).

Frequency, severity, and causal relationship of adverse events will be tabulated by system organ class and preferred term after coding according to the current version of the Medical Dictionary for Drug Regulatory Activities (MedDRA) at database lock.

Note that AEs occurring after the last per protocol contact but entered before database lock will be reported to Pharmacovigilance only and will not be captured in the trial database (See section [5.2.7.2.1](#)).

Laboratory data will be analysed both quantitatively as well as qualitatively. The latter will be done via comparison of laboratory data to their reference ranges. Values outside the reference range as well as values defined as clinically relevant will be summarised. Treatment groups will be compared descriptively with regard to distribution parameters as well as with regard to frequency and percentage of subjects with abnormal values or clinically relevant abnormal values.

Vital signs, physical examinations, or other safety-relevant data observed at screening, baseline, during the course of the trial and at the end-of-trial evaluation will be assessed with regard to possible changes compared to findings before start of treatment.

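### The commitment to notify investigators of SUSARs ends 30 days after LPLT at their site, before the last-dosed subject there completes follow-up of 84 days (Part B) or 98 days (Part A)

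*Protocol*

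**What the plan says.** Protocol 8.6 sets the end of SUSAR notification to sites: "Individual investigators will be notified of SUSARs occurring with the trial medication until 30 days after LPLT at their site". It gives no reason for 30 days. The same section says that the LPLT "date is defined as the date on which the last subject in the whole trial is administered the last dose of trial treatment", so the term is defined for the trial as a whole but used per site.

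Other sections set a longer safety horizon:

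- **Dosing visits** (6.2.2): "Visit 2 for Part A and Visits 2, 3 and 4 for Part B".
- **Follow-up.** For Part B, 3.1 says subjects "will be observed for safety and efficacy for 12 weeks after the last injection". For Part A, 1.4.2.5 gives up to 98 days.
- **AE collection** (5.2.7.2.1): all AEs and AESIs from consent to the EOS visit.
- **AE analysis** (7.3.5): for this drug, "the residual effect period (REP) after IVT administration is not known", so AEs with onset up to EOS are assigned to the on-treatment period.
- **Expected duration of action** (4.1.2): the proposed therapeutic dose "is predicted to maintain the minimal efficacious vitreal concentration of 1000 pM (1 nM) for three months".

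No section of the protocol or SAP commits to notifying individual investigators of SUSARs beyond the point set in 8.6.

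**The concern.** The 30-day limit does not match the period over which the protocol itself looks for drug effects. The investigator must observe subjects and report their events to the sponsor until EOS. The sponsor's stated commitment to send SUSARs in the other direction can lapse well before that.

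This is a first-in-human intravitreal drug. An investigator with a subject still in follow-up has reason to know of an unexpected serious reaction elsewhere: to look for it, to inform the subject, and to weigh it before a further invasive study procedure. Optional aqueous sampling at Part B Visits 6 and 7 is one such procedure, and both visits fall after the nominal end of the commitment for a site's last-dosed subject.

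**Working it through.** **Inputs (nominal days)**

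| Quantity | Part A | Part B | Source |
|---|---|---|---|
| Last planned dose | Day 1 | Day 57 (Visit 4) | Protocol 6.2.2, Tables 4.1.4: 1 and 4.1.4: 2 |
| EOS | Day 99 (Visit 8) | Day 141 (Visit 7) | Flow Charts I and II; SAP Tables 6.7: 1 and 6.7: 3 |
| Notification after site LPLT | 30 days | 30 days | Protocol 8.6 |

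**Step 1: reproduce the plan's follow-up periods.** Follow-up = EOS day − last dose day.
- Part B: 141 − 57 = 84 days = 12 × 7, matching the 12 weeks in 3.1.
- Part A: 99 − 1 = 98 days, matching 1.4.2.5.

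**Step 2: the gap for the last-dosed subject at a site.** Gap = follow-up − 30.
- Part B: the commitment ends on Day 57 + 30 = Day 87. Gap = 84 − 30 = 54 days; 54/84 = 64%. Visit 5 (Day 85) is inside; Visits 6 (Day 113) and 7 (Day 141) are outside.
- Part A, if no later dose is given at the site: the commitment ends on Day 1 + 30 = Day 31. Gap = 98 − 30 = 68 days; 68/98 = 69%. Visit 6 (Day 29) is inside; Visits 7 (Day 57) and 8 (Day 99) are outside.

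**Step 3: visit windows.**
- Part B (Visit 4 ±3 days, EOS ±7 days): follow-up runs from 74 to 94 days, so the gap is 44/74 = 59% to 64/94 = 68%.
- Part A (EOS ±7 days): follow-up runs from 91 to 105 days, so the gap is 61/91 = 67% to 75/105 = 71%.

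**Step 4: subjects dosed earlier at the same site.** If a Part B subject's last dose was g days before the site's last dose, the gap is max(0, 84 − g − 30) = max(0, 54 − g).

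| g (days) | Gap (days) | Share of 84 |
|---|---|---|
| 0 | 54 | 64% |
| 14 | 40 | 48% |
| 28 | 26 | 31% |
| 54 or more | 0 | 0% |

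The Part A analogue is max(0, 68 − g). Under 3.1, Part B starts at least 14 days after the final Part A dose, and its third injection is 57 − 1 = 56 days after its first. A Part A subject at a site that later gives a full Part B course therefore has g of at least 14 + 56 = 70, which exceeds 68, and so has no gap on nominal timing.

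**Step 5: early stopping of treatment.** If the site's last Part B dose was given on Day 29 or Day 1 to a subject who stays to Day 141, the gap is (112 − 30)/112 = 82/112 = 73%, or (140 − 30)/140 = 110/140 = 79%.

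**Step 6: the other reading of LPLT.** If LPLT means the last dose in the whole trial, sites that finish dosing earlier are covered for longer. The site of the last-dosed Part B subject still has the 54-day gap.

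**Step 7: after the change.** With notification to the last subject's EOS at each site, the gap is 0 days in both parts.

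**The case against.** The strongest case on the other side is that 8.6 does not stand alone.

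- **Stopping rule (3.3.4.3).** One serious adverse reaction, confirmed as related by both investigator and sponsor, interrupts Part A enrolment and further Part B treatment. Restart after such a stop needs regulatory approval through a substantial amendment. A SUSAR confirmed by both would therefore affect the whole trial.
- **Benefit-risk review (3.3.4.1), re-consent (8.1), regulatory reporting (8.4) and sponsor and SMC oversight (8.7).** Each is a route by which important safety information could reach sites.
- **No dosing decision is at stake at the affected site**, because its last dose has been given. Aqueous sampling is optional and needs separate consent.
- **Low event count so far.** Protocol 1.2 reports no DLEs and no drug-related AEs or SAEs in the first seven subjects treated.

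Much of this stands. A reader might infer from 8.6 that investigators would not hear of a SUSAR, or that the plan withholds it. The documents do not support that: 8.6 sets where a commitment ends and forbids no later communication. Even so, none of the provisions says that an investigator whose subjects are only in follow-up will be told. The stopping rule acts on enrolment and treatment, and does not cover a SUSAR judged related by only one party. Participating investigators sit on the SMC for Part A only, and only as deemed necessary.

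Three other inferences go too far:

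- **That two thirds of all subjects' follow-up is uncovered.** The share belongs to the last-dosed subject at each site. Protocol 3.3 says: "It is planned to conduct the trial in up to 3-6 countries and at approximately 50 sites". With about 48 subjects, that is 48/50, or about one per site, so the last-dosed subject may often be the only one. But this is a planning average under competitive screening. Sites that treat no one have no last dose, and no per-site enrolment is given.
- **That 7.3.5 declares subjects exposed to EOS.** It assigns events to a period for analysis because the residual effect is unknown. It makes no pharmacological statement.
- **That the Part B primary endpoint is distorted.** Causality under 5.2.7.1.6 rests on many factors. SUSAR notices are not among those named, and nothing in the documents allows an effect to be estimated.

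**Conclusion.** The point holds as a gap in a stated commitment. On the planned schedule, up to 54 of 84 post-dose days (64%) in Part B fall outside it for the last-dosed subject at a site. Where the site's last dose was a Part A dose, the figure is 68 of 98 days (69%). These figures use nominal visit days, LPLT read site by site, the full planned course and no later dose at the site. They count calendar days, not expected SUSARs. For subjects dosed earlier at the site, the gap shrinks and reaches zero at 54 days (Part B) or 68 days (Part A) before the site's last dose.

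The double use of LPLT is a separate, smaller defect in the same section. Neither shows a breached requirement or a biased endpoint. This is an inexpensive improvement to subject safety, worth making because the other safeguards narrow the gap without closing it.

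**What to change.** In Protocol 8.6, replace the notification sentence with one to this effect: each investigator will be notified of SUSARs occurring with the trial medication until the last subject at that site has completed the EOS visit, and for not less than 30 days after the last dose given at that site.

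This ties the end date to follow-up at the site and keeps 30 days as a minimum. By referring to the last dose given at the site instead of LPLT, it leaves the whole-trial definition of LPLT free for milestone reporting.

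The cost is one sentence in an amendment and a later end date on the SUSAR distribution list. The downside is a few more notices to sites. No visit, assessment, sample size or analysis changes.
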